2.4.4.1 Analysis of primary and additional efficacy endpoint(s)

The analysis of primary endpoint of sustained remission at Week 52 will be limited to the cohort of patients who had an opportunity to complete the 52-week treatment period (i.e., Week 52 Analysis set).

The proportion of patients achieving sustained remission at Week 52 will be summarized using counts and percentages by the 4 treatment groups. In addition, the treatment effects between the combined sarilumab (group A+B) group and the combined placebo group (Group C+D) will be compared using a Cochran-Mantel-Haenszel (CMH) test stratified by prednisone dose at baseline (<30 mg/day or ≥30 mg/day).

The additional endpoint of sustained remission at Week 24 will be analyzed in the same fashion in the ITT population.

Sensitivity analysis excluding acute phase reactants:

Sensitivity analysis will be performed for the primary endpoint by removing the acute phase reactants (CRP and ESR) from the definition to mitigate against the possibility of biasing the results due to the known PD effect of sarilumab on acute phase reactants.

Patients achieving sustained remission at Week 52 (or Week 24) excluding acute phase reactants is defined by having met all of the following parameters:

- Achievement of disease remission not later than Week 12. **Disease remission** is defined as resolution of signs and symptoms of GCA.
AND
- Absence of disease flare from Week 12 through Week 52 (or Week 24). **Flare** is defined as recurrence of signs and symptoms attributable to active GCA plus an increase in CS dose due to GCA.
AND
- Successful adherence to the prednisone taper from Week 12 through Week 52 (or Week 24).

The sensitivity analysis will be performed in the same fashion as for the primary endpoint. Descriptive statistics (i.e., counts and percentages) will be provided for the three individual components.

Subgroup analyses:

No subgroup analyses will be performed due to the small sample size.

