- Constitutional syndrome, including but not limited to fever, malaise, unintentional weight loss, night sweat, asthenia, fatigue, loss of appetite.
- New or worsened extremity claudication, bruits and asymmetrical pulses.
- Other features judged by the Investigator to be consistent with a GCA or PMR flare.

The resolution of signs and symptoms of GCA is identified in eCRF “GCA Assessment” page with the question “Based upon the patient’s relevant medical history and the clinical assessment and responses provided above, does the patient have active GCA?” ticked as “No”. The resolution of signs and symptoms of GCA by Week 12 will be determined based on the last non-missing post-baseline GCA assessment measured up to Week 12.

Patients who took rescue CS due to active GCA prior to Week 12 or who permanently withdraw from the study treatment prior to Week 12 will be considered as not achieved disease remission by Week 12.

2. Absence of disease flare from Week 12 through Week 52.

Flare is defined as either 1) recurrence of signs and symptoms attributable to active GCA plus an increase in CS dose due to GCA, or 2) elevation of ESR attributable to active GCA plus an increase in CS dose due to GCA. Increase in CS dose is defined as:

- Any dose increase during the protocol defined steroid taper, or
- Reinitiation of prednisone therapy after the protocol defined taper has been completed.

Patients with disease flare are identified as those with the reason for treatment ticked “rescue therapy” in eCRF “Steroid Medication” page and to the question “If Rescue Therapy, please specify” ticked either “Active GCA” or “Elevated ESR Attributable to Active GCA”.

3. Normalization of CRP (to <10 mg/L, with an absence of successive elevations to ≥10 mg/L) from Week 12 through Week 52

The status of normalization of CRP from Week 12 through Week 52 will be determined based on the CRP values measured at Week 16, Week 20, Week 24, Week 32, Week 40 and Week 52. If there are two or more consecutive visits with CRP ≥10 mg/L, then it is categorized as no normalization of CRP. Intermittent missing CRP at Week 16, Week 20, Week 24, Week 32, Week 40 or Week 52 will be imputed using last value carried forward (LOCF) approach.

4. Successful adherence to the prednisone taper from Week 12 through Week 52

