Successful adherence to the prednisone taper from Week 12 through Week 52 is defined as patients did not take rescue therapy from Week 12 through Week 52 and may include the use of any excess prednisone (beyond the per protocol CS tapering regimen) with a cumulative dose of ≤100 mg (or equivalent), such as those employed to manage AE not related to GCA. The cumulative dose of excess prednisone use will be counted from baseline to Week 52.

In addition, patients who permanently withdraw from the study treatment prior to Week 52 will be considered as not achieved component 2, 3, or 4 for the primary endpoint.

Additional Endpoint: Sustained remission at Week 24

Based on patients’ enrollment dates and the study discontinuation plan, all patients would have had the opportunity to be treated for at least 24 weeks. As a result, an additional endpoint, sustained remission at Week 24, which is defined similarly as the primary endpoint but with shorter sustained period, is added in the SAP.

The sustained remission at Week 24 is defined by having met all of the following parameters:

- Achievement of disease remission not later than Week 12,
- Absence of disease flare from Week 12 through Week 24,
- Normalization of CRP (to <10 mg/L, with an absence of successive elevations to ≥10 mg/L) from Week 12 through Week 24, and
- Successful adherence to the prednisone taper from Week 12 through Week 24.

Components of the sustained remission at Week 24 are described as below:

- 1. Achievement of disease remission not later than Week 12**, which is defined in the same way as described for the primary endpoint.
- 2. Absence of disease flare from Week 12 through Week 24**, where disease flare is defined in the same way as described for the primary endpoint.
- 3. Normalization of CRP (to <10 mg/L, with an absence of successive elevations to ≥10 mg/L) from Week 12 through Week 24**

The status of normalization of CRP from Week 12 through Week 24 will be determined based on the CRP values measured at Week 16, Week 20, Week 24. If there are two or more consecutive visits with CRP ≥10 mg/L, then it's categorized as no normalization of CRP. Intermittent missing CRP at Week 16, Week 20 or Week 24 will be imputed using last value carried forward (LOCF) approach.

4. Successful adherence to the prednisone taper from Week 12 through Week 24

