Successful adherence to the prednisone taper from Week 12 through Week 24 is defined as patients did not take rescue therapy from Week 12 through Week 24 and may include the use of any excess prednisone (beyond the per protocol CS tapering regimen) with a cumulative dose of ≤100 mg (or equivalent), such as those employed to manage AE not related to GCA. The cumulative dose of excess prednisone use will be counted from baseline to Week 24.

In addition, patients who permanently withdraw from the study treatment prior to Week 24 will be considered as not achieved component 2, 3, or 4 for the primary endpoint.

Blinding of CRP and ESR assessment results

Investigators, including Efficacy Assessors, and patients will remain blinded to CRP and ESR results (except screening and baseline). Safety Assessors will also be blinded on post baseline CRP but will have access to ESR results.

ESR kits will be provided by the central laboratory while the test will be performed locally at site, results (the distance in millimeters (mm) that red blood cells has descended in 1 hour) will be blinded to Investigators including Efficacy Assessors and staff directly involved in efficacy assessment of study patients.

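### For rescue from Week 12 on, dropping ESR from the sensitivity analysis cannot change any patient's composite status, so only CRP is effectively removed

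*SAP*

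**What the plan says.** SAP 2.4.4.1 states the aim as "removing the acute phase reactants (CRP and ESR) from the definition", to mitigate the "possibility of biasing the results due to the known PD effect of sarilumab on acute phase reactants". Three requirements remain, for Week 52 and for Week 24:

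- remission by Week 12, now judged on signs and symptoms only;
- no flare, with flare now limited to the signs-and-symptoms limb;
- adherence to the prednisone taper, carried over with no new definition.

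The result is analysed like the primary endpoint, including the stratified comparison of pooled arms, and counts are given for each of the three components.

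The underlying definitions are in SAP 2.1.3.1. ESR enters the composite through the second limb of flare: "elevation of ESR attributable to active GCA plus an increase in CS dose due to GCA". On derivation the SAP says: "Patients with disease flare are identified as those with the reason for treatment ticked" as rescue therapy on the steroid page, with a sub-reason of either active GCA or "Elevated ESR Attributable to Active GCA". Adherence to Week 52 "is defined as patients did not take rescue therapy from Week 12 through Week 52". The Week 24 version "is defined as patients did not take rescue therapy from Week 12 through Week 24". Neither makes an exception by reason for rescue. Adherence also tolerates up to 100 mg of cumulative excess prednisone counted from baseline, "such as those employed to manage AE not related to GCA".

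**The concern.** ESR sits in the composite twice: openly in the flare definition, and again through the rescue record that adherence reads. The sensitivity definition removes only the first. The second still fails the same patients.

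This matters because the analysis exists to show whether the result depends on markers that sarilumab acts on directly. If ESR prompts rescue more often in patients not on sarilumab, which is what the SAP's rationale implies, those failures stay in the comparison and favour sarilumab. Readers would take the result as free of ESR influence. Protocol 11.4.2.1 promises a sensitivity analysis without acute phase reactants, and Protocol 11.1 and SAP 1.3 say the sample size was chosen partly to power such analyses.

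**Working it through.** The plan states no figure to reproduce here. The check is one of logic, followed by a size per patient.

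**Set argument, rescue from Week 12 on.** Let S be resolution of signs and symptoms by Week 12, A a flare ticked as active GCA, E a flare ticked as elevated ESR, R any rescue, and N non-adherence.

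1. E is contained in R, because an ESR flare is a sub-reason of a rescue entry.
2. R is contained in N, because adherence requires no rescue.
3. Sensitivity responder with the ESR limb kept: S, and not A, and not E, and not N.
4. Sensitivity responder with the ESR limb dropped: S, and not A, and not N.
5. Since E lies inside N, not-N already implies not-E. Lines 3 and 4 select the same patients. The same holds with the CRP requirements added back.

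**Enumeration.** Code every patient as signs and symptoms resolved by Week 12 (2) × CRP normal by Week 12 (2) × CRP sustained (2) × rescue reason: none, active GCA, ESR, other (4) × excess prednisone above 100 mg (2) × treatment withdrawal (2) = 128 states.

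| Comparison | States that change |
|---|---|
| Composite, ESR limb kept vs dropped (with or without CRP) | 0 |
| Flare component alone, ESR limb kept vs dropped | 32 (= 128/4) |
| Primary composite vs sensitivity composite | 3, all without rescue and all due to CRP |
| Sensitivity composite, ESR-only rescue counted vs exempted | 4 |

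The 4 states in the last row are those with signs and symptoms resolved, ESR-only rescue, no excess above 100 mg and no withdrawal, with any of the four CRP patterns. These are counts of possible states, not of patients. They also show that waiving the rescue tick alone is not enough: if the rescue dose itself exceeds 100 mg, the excess limit still fails the patient.

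**Size per patient.** SAP Table 1 gives 41 pooled placebo patients for Week 24. SAP 2.3.1 gives 36 patients for Week 52 without the split by arm, so 18 per pooled arm is assumed.

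| ESR-only rescues meeting all other components, one arm | Week 24 (k/41) | Week 52 (k/18, assumed) |
|---|---|---|
| 0 | 0 | 0 |
| 1 | 2.4 points | 5.6 points |
| 2 | 4.9 points | 11.1 points |
| 3 | 7.3 points | 16.7 points |

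If the Week 52 arm held 14 or 22 patients instead of 18, one patient would be worth 1/14 = 7.1 or 1/22 = 4.5 points.

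**The case against.** **ESR-only rescue should be uncommon.** Under Protocol 10.1 the Efficacy Assessor, who manages rescue, works without ESR by default. This stands as a limit on size. It does not remove the point, because the same section lets the assessor ask for the last ESR value or obtain a local one when a decision absolutely requires it, and the case report form has a dedicated option for this reason.

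**A rescued patient really has left the taper.** Protocol 9.6 makes adherence part of what the endpoint is for, Protocol 11.4.2.1 counts open-label prednisone rescue as nonresponse, and Protocol 8.2 bars return to the taper. Counting such patients as responders answers a different question. This is a good reason to keep the current version. It does not support describing that version as having ESR removed.

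**The 100 mg allowance might cover these patients.** It is joined to the no-rescue condition and does not waive it.

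**Everything is descriptive.** SAP 2.4.4 and 2.4.4.3 say so, and no decision rule rests on this analysis. That limits the severity.

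Two stronger readings are tempting. A reader might infer that the sensitivity analysis reclassifies nobody. The documents do not support that: removing CRP changes responder status, and the stand-alone flare count responds to the loss of the ESR limb. A reader might also infer that every ESR-triggered rescue, at any time, fails adherence. Component 4 covers rescue only from Week 12. Earlier rescue falls under the remission rule in SAP 2.1.3.1, which refers to rescue for active GCA and does not say whether the ESR tick counts, or whether the rule carries into the sensitivity definition.

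**Conclusion.** The point holds for the composite at Week 52 and Week 24, for rescue from Week 12 on. The announced removal of ESR changes no patient's responder status, whatever the data. Only the removal of CRP has effect there.

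The shifts of about 2.4 points (Week 24) and 5.6 points (Week 52, assumed even split) apply only to a patient who has signs and symptoms resolved by Week 12, no signs-and-symptoms flare, no treatment withdrawal, and no other excess prednisone above the limit. Any other ESR-rescued patient moves nothing.

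A reader might go further and conclude that the sensitivity result is biased towards sarilumab by a known amount. The documents give no count of ESR-only rescues, overall or by arm, so neither the size nor the realised direction can be stated. This is a mismatch between a stated property and the derivation in one descriptive analysis. It should be corrected, and it does not affect the primary analysis.

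**What to change.** For Week 52 and Week 24:

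1. Add a version of the sensitivity composite in which rescue whose only ticked reason is "Elevated ESR Attributable to Active GCA" does not count as non-adherence, and in which the steroid dose given for that rescue does not count toward the 100 mg excess limit. Leave all other components unchanged.
2. Report it beside the current version. State that the current composite still counts ESR-triggered rescue as failure, so that only CRP is effectively removed from it. Do not simply rename the current analysis as excluding CRP, because its flare component does drop ESR.
3. Give the number of ESR-only rescues by arm. If it is zero, the two versions coincide and the matter is closed.

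The cost is one derivation from an existing case report form field, one further run and a few lines of text. The downside is that patients given extra steroid may count as responders in the added version, which is why both are shown. The change concerns endpoint derivation only and leaves the management of rescue untouched.

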2.4.4.2 Analyses of secondary efficacy endpoints

Components of sustained remission composite measure at Week 52 and Week 24

Descriptive statistics (i.e., counts and percentages) will be provided for the following binary variables by treatment groups:

- Patients who achieve disease remission by Week 12
- Patients who have absence of disease flare from Week 12 through Week 52 (or Week 24)
- Patients who have normalization of CRP (decrease to <10 mg/L) with sustained normalization from Week 12 through Week 52 (or Week 24)
- Patients who successfully adhere to the prednisone taper from Week 12 through Week 52 (or Week 24)

Total cumulative corticosteroid (including prednisone) dose

Descriptive statistics including the number of subjects, mean, and median of the total cumulative prednisone (or equivalent) dose will be presented for each treatment group. The difference between the medians and the corresponding 95% non-parametric confidence interval along with

p-value from the non-parametric Wilcoxon rank-sum test between the two combined treatment groups will also be provided.

The total cumulative CS dose will be based on the total number of days with complete or partial intake, no imputation will be done on missed tablets. Patients who received increased prednisone or equivalent in rescue therapy will be included in their original treatment groups.

In the scenario that a patient has already taken external CS for the disease before randomization on the day of randomization, the CS dose taken will be considered as the first dose of oral IMP. The first dose of prednisone per tapering regimen will be skipped, and the patient will take the second dose of prednisone on the next day.

Time to first GCA flare during the treatment period

Time (from randomization) to the first GCA flare after clinical remission up to Week 52 will be analyzed by Kaplan-Meier method providing the median, 25th and 75th percentiles (where possible) along with the 95% CI for the median. The comparison between the two combined groups will be performed using Cox proportional hazards model with prednisone dose at baseline (<30 mg/day or ≥30 mg/day) included as a covariate. Hazard ratio and the corresponding 95% CI and p-value will be provided.

Composite GTI and Specific List

GTI analyses

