11.4.2.2 Analyses of secondary efficacy endpoints

Other binary endpoints will be analyzed as described for the primary endpoint.

The cumulative prednisone dose will be analyzed using a nonparametric van Elteren test stratified by baseline prednisone dose and the mean and median dose will be summarized.

Time events will be analyzed by Kaplan-Meier method. Treatment groups will be compared with the use of Cox proportional hazards models, with adjustment for the baseline prednisone dose. Data censoring will be used for patients who withdraw from the study.

The GTI assessment (total score and domain-specific scores) will be analyzed with a mixed model repeated measures (MMRM) approach. The model, including treatment, visit, treatment-by-visit interaction, baseline prednisone dose (< 30 mg/day or ≥ 30 mg/day) as fixed effects and baseline score as a covariate, will be used to test the difference of least-square means (LS means) between treatment groups. Descriptive statistics including number of subjects, mean, standard error and LS means will be provided. In addition, difference in LS means, the corresponding 99% CI and the p-value will be provided.

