1.1 STUDY DESIGN AND RANDOMIZATION

Original study design

This is a multicenter, randomized, double-blind, placebo controlled 52-week Phase 3 study with a 24-week post-treatment follow up phase, evaluating the efficacy and safety of sarilumab in patients with giant cell arteritis (GCA).

Approximately 360 patients with GCA (new onset or refractory [eg, disease relapse] GCA) who meet the entry criteria will be randomized to 4 parallel treatment groups with sarilumab 200 mg q2w, 150 mg q2w, or placebo q2w plus 26-week prednisone taper, or placebo q2w with 52-week standardized prednisone taper at a ratio of 2:1:1:2 as described below. Randomization will be stratified by the starting dose of prednisone at baseline (<30 mg/day or ≥30 mg/day) using a block randomization schedule, and aim to enroll at least 30% of new onset patients by capping enrolment of refractory patients to ≤70% of total patients randomized.

- Treatment Group A: sarilumab 200 mg q2w with a 26-week taper of CS.
- Treatment Group B: sarilumab 150 mg q2w with a 26-week taper of CS.
- Treatment Group C: sarilumab matching placebo q2w with a 26-week taper of CS.
- Treatment Group D: sarilumab matching placebo q2w with a 52-week taper of CS.

It is important to optimize CS treatment prior to randomization to minimize the risk of adverse sequelae from GCA. Patients will be dosed with prednisone between 20 to 60 mg/day at the time of randomization (baseline) and initiate a taper according to the protocol defined schedule. Patients will be initiated on a standardized taper of prednisone from the time of randomization.

The taper will initially be open label; patients will have between 1 to 7 weeks to taper prednisone dose to 20 mg/day following randomization.

The further tapering of prednisone once a dose of 20 mg/day is achieved will be done in a blinded manner. To achieve the appropriate daily dose during this phase, patients will receive a combination of prednisone and/or placebo to prednisone depending on the assigned treatment group and associated taper regimen.

The total tapering period (open label plus double blind prednisone periods) will be between 46 weeks to 52 weeks depending on the initial prednisone dose at randomization.

At each site visit, the patient's disease will be assessed to determine whether the patient can adhere to the protocol defined prednisone taper schedule.

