Appendix C Summary of statistical analyses

Endpoint	Analysis		Statistical	Supportive	Subgroup	Other
	Population	Primary Analysis	Method	Analysis*	Analysis*	Analyses*
Primary Endpoint						
Patients who achieved sustained remission at Week 52	ITT	Proportion of patients achieving sustained remission at Week 52	CMH test stratified by baseline prednisone dose for combined groups, and descriptive analysis for non-combined groups.	1) Sensitivity analysis;2) Analysis excluding patients who prematurely withdraw from the study due to early termination of the study	No	No
Additional endpoint: Patients who achieved sustained remission at Week 24	ITT	Proportion of patients achieving sustained remission at Week 24	CMH test stratified by baseline prednisone dose for combined groups, and descriptive analysis for non-combined groups	Sensitivity analysis	No	No
Secondary Endpoints						
Patients who achieved of disease remission by Week 12	ITT	Proportion of patients who achieved of disease remission by Week 12	Descriptive	No	No	No
Patients who have absence of disease flare from Week 12 through Week 24 and Week 52	ITT	Proportion of patients who have absence of disease flare from Week 12 through Week 24 and Week 52	Descriptive	No	No	No
Patients who have normalization of CRP (decrease to <10 mg/L) with sustained normalization from Week	ITT	Proportion of patients who have normalization of CRP (decrease to <10 mg/L) with sustained normalization from Week 12 through Week 24 and Week 52	Descriptive	No	No	No

Endpoint	Analysis		Statistical	Supportive	Subgroup	Other
	Population	Primary Analysis	Method	Analysis*	Analysis*	Analyses*
12 through Week 24 and Week 52						
Patients who successfully adhere to the prednisone taper from Week 12 through Week 24 and Week 52	ITT	Proportion of patients who successfully adhere to the prednisone taper from Week 12 through Week 24 and Week 52	Descriptive	No	No	No
Total cumulative prednisone (or equivalent) dose	ITT	Total cumulative prednisone (or equivalent) dose over 52-week treatment period	Descriptive	No	No	No
Time to the first GCA flare after clinical remission up to Week 52	ITT	Time (from randomization) to the first GCA flare after clinical remission up to Week 52	Kaplan-Meier estimates and Cox proportional hazards model for combined groups, and descriptive analysis for non-combined groups.	No	No	No

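### The SAP replaces the protocol's stratified van Elteren test of cumulative steroid dose with an unstratified rank-sum test and does not list the change; the result is somewhat less precise, not biased

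*SAP*

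**What the plan says.** Protocol 11.4.2.2 states: "The cumulative prednisone dose will be analyzed using a nonparametric van Elteren test stratified by baseline prednisone dose". The protocol synopsis names the same test. In Protocol 11.4.2.3 this is the first secondary endpoint in the testing sequence after the primary comparisons.

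SAP 2.4.4.2 plans "The difference between the medians and the corresponding 95% non-parametric confidence interval", together with a "p-value from the non-parametric Wilcoxon rank-sum test between the two combined treatment groups". It names no stratification for either.

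SAP 1.1 repeats the design: "Randomization will be stratified by the starting dose of prednisone at baseline" (<30 or ≥30 mg/day). The SAP's other between-group analyses use that factor:

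- CMH for sustained remission (SAP 2.4.4.1): "test stratified by prednisone dose at baseline".
- Time to first flare (SAP 2.4.4.2): "Cox proportional hazards model with prednisone dose at baseline" as a covariate.
- ANCOVA for the two cumulative glucocorticoid toxicity scores (SAP 2.4.4.2): baseline prednisone dose as a fixed effect.

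SAP 1.6 sets out the changes from the protocol's analysis plan. It covers the Week 52 cohort, the Week 24 endpoint, missing-data handling, pooled comparisons with 95% intervals, nominal p-values, and the removal of the hierarchy and subgroups. It does not mention the van Elteren test or its stratification.

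In SAP Appendix C the row for "Total cumulative prednisone (or equivalent) dose over 52-week treatment period" gives the method only as descriptive. That does not match the test and interval in SAP 2.4.4.2.

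**The concern.** Two things look wrong.

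The first is traceability. A prespecified stratified test became an unstratified one, with no entry in the list of changes and no reason given. Small numbers cannot be the reason, because the CMH test keeps the same two strata even in the 36-patient Week 52 set.

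The second is efficiency. Of all the tested endpoints, this is the one where the stratum acts most directly, because the starting dose is itself part of the total being measured. Stratified blocked randomisation balances the strata between arms. An unstratified rank test still counts the between-stratum spread as noise. Its standard error is then too large, the test is conservative, and the interval is wider than it need be.

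What is at stake is the precision of the steroid-sparing estimate. In an analysis declared descriptive, the interval is the part readers will use.

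**Working it through.** **Plan figures.** Neither document gives a power or precision figure for cumulative dose. The nearest is SAP Table 1 for the same pooled groups (42 against 41) on Week 24 remission. Its 82.3% and 94.5% reproduce with a two-sided pooled-variance chi-square calculation, but they say nothing about dose.

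**Step 1. Scheduled totals from Protocol Appendix B** (7 × the sum of the weekly daily doses).

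| Start (mg/day) | 20 | 25 | 30 | 35 | 40 | 50 | 60 |
|---|---|---|---|---|---|---|---|
| 26-week taper (mg) | 952 | 1,127 | 1,337 | 1,582 | 1,862 | 2,212 | 2,632 |
| 52-week taper (mg) | 2,212 | 2,387 | 2,597 | 2,842 | 3,122 | 3,472 | 3,892 |

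For example, the 20 mg column of the 26-week table sums to 136, and 7 × 136 = 952. Starting dose moves the total by 2,632 − 952 = 1,680 mg within either taper. Taper length moves it by 1,260 mg at every starting dose.

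**Step 2. Size of the stratum effect.** The documents do not give the starting-dose mix, so assume the seven doses are equally frequent. The ≥30 mean is (1,337 + 1,582 + 1,862 + 2,212 + 2,632)/5 = 1,925 mg on the 26-week taper. The <30 mean is (952 + 1,127)/2 = 1,039.5 mg. The difference is 885.5 mg. The variance due to starting dose is 312,150 mg². The part between the two strata is (5/7)(2/7)(885.5²) = 160,022 mg².

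**Step 3. A calculation on means for the planned contrast.** SAP Table 1 has 14 patients in C and 27 in D, so taper length adds 1,260² × (27/41)(14/41) = 356,998 mg² of variance within C+D. Let V be the variance of rescue and other extra dose (assumed, the same in all groups).

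- Unstratified: (312,150 + V)/42 + (312,150 + 356,998 + V)/41
- Stratified: the same, with 160,022 subtracted from each numerator

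The square root of their ratio approximates the ratio of interval widths.

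| Assumed SD of extra dose (mg) | SE unstratified (mg) | SE stratified (mg) | Ratio |
|---|---|---|---|
| 0 | 154 | 127 | 1.22 |
| 300 | 168 | 143 | 1.17 |
| 500 | 189 | 168 | 1.13 |
| 800 | 234 | 217 | 1.08 |

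**Step 4. Simulation with the rank methods.** There were 83 patients, randomised 2:1:1:2 in blocks within stratum, with Appendix B doses. The van Elteren statistic is Σ w_h [R_h − n_1h(n_h + 1)/2] with w_h = 1/(n_h + 1), where R_h is the rank sum of the sarilumab patients in stratum h. It is divided by its permutation standard error.

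- Interval width, A+B against C+D. Assumed: three starting-dose mixes; rescue in 35, 40, 70 and 60% of A, B, C and D; median extra dose 400 or 800 mg; with and without 47 of 83 patients stopping at Weeks 24 to 51. The unstratified interval was 1.12 to 1.19 times as wide (635–807 mg against 571–709 mg). Other assumption sets gave 1.11 to 1.17 and 1.08 to 1.16.
- Power at two-sided 0.05, same contrast. Assumed: rescue rates 20 to 50%; mean rescue dose 500 to 2,000 mg; missed doses 0 to 5%; with and without early stopping. Power was 0.88 to 1.00 for the rank-sum test and 0.93 to 1.00 for van Elteren, a gain of 0 to about 4.5 percentage points.

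**The case against.** The strongest reply is that little turns on this. The trial stopped at 83 of 360 patients, efficacy is declared descriptive, and all p-values are nominal without multiplicity control. A conservative test cannot manufacture a steroid-sparing claim, and stratified randomisation protects against bias. SAP 1.6 also announces pooled tests with 95% intervals and refers to SAP 2.4.4 for details, so the change is partly signposted. All of this stands, and it limits the weight of the point. It does not explain why only this comparison lost the stratum, and the reference to 2.4.4 does not say that stratification was dropped.

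A reader might infer more than the documents support:

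- *That starting dose is the strongest predictor of cumulative dose.* Neither document says so. With equally frequent starting doses and 27 of 83 patients in Group D, starting dose carries about 47% of the scheduled-dose variance and taper length about 53%, before any rescue dose.
- *That the planned test runs far below its nominal level, or that much power is lost.* A markedly sub-nominal level appears when all patients follow one taper. In the planned contrast 27 of 41 controls are on the longer taper, so that null cannot occur. A large power loss would concern A+B against C alone, and SAP 2.4.4 rules out formal comparisons between individual groups.
- *That the SAP pairs a difference of sample medians with a Hodges-Lehmann interval.* It calls the interval non-parametric and does not say how it is built, so a mismatch cannot be shown. The method is unspecified.

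**Conclusion.** The point holds as an undeclared departure from the protocol with a modest cost in precision. The planned analysis is conservative and less efficient, not biased. For A+B against C+D the 95% interval is roughly 1.1 to 1.2 times as wide as the stratified one. Power is little changed, because Group D's longer taper dominates the contrast. These sizes rest on assumed starting-dose mixes, rescue rates and rescue doses, none of which the documents give. The departure from the protocol, the missing entry in SAP 1.6 and the Appendix C mismatch rest on the text alone. No confirmatory decision is affected.

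**What to change.** In SAP 2.4.4.2, restore the van Elteren test stratified by baseline prednisone (<30 / ≥30 mg/day) for A+B against C+D. Report a stratified Hodges-Lehmann shift with the 95% interval obtained by inverting that test, so that estimate, interval and p-value belong together. Group medians can stay as descriptive statistics. Enter the same method in the Appendix C row for this endpoint. If the sponsor prefers the unstratified test, SAP 1.6 should list the change and give the reason.

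The cost is a few sentences of SAP text and a few lines of code. The stratum is already recorded and used elsewhere in the SAP, so no new data are needed.
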